The analysis will be based on random effects (RE) models applied to baseline and all follow-up visits at which outcome data are collected. The RE will be included to account for correlated and missing data. Separate time effects and time-treatment interactions will be specified for each follow-up visit, such that the treatment-time interaction for a particular visit will be the ITT effect on change since baseline. The RE models will be linear, logistic, and log-linear for continuous, binary, and count outcomes, respectively. Similar RE models will be employed for assessment of mediation and moderation in Secondary Aims 1 and 2.

**Data description, screening, and reorganization:** We will screen data for quality and integrity as proposed by Altman. For all variables we will determine measures of central tendency: mean and standard deviation for continuous variables, median and range for categorical variables. We will examine frequency distribution graphically (histograms, scatter plots) for all variables. Specific concerns will be directed to understanding the pattern of missing values, isolating outliers, confirming the homoscedasticity of observation groups, verifying the coding consistency, examining adherence to normality for variables anticipated to be so, and locating normalizing transformations for continuous variables intended to be investigated as such. For the tools we developed, we will examine internal consistency using Cronbach's  $\alpha$ .

**Addressing the impact of site on each outcome:** First, we will pool participants across sites, assuming no site effect, using logistic and regression modeling to isolate the relationship between outcome and exposure and other demographics. We have stratified randomization to analyze the effect of site. We have amplified the sample size (D.10) to have a large enough sample to conduct this analysis. As a secondary analysis, we will examine treatment-site interactions. In the presence of statistically significant interactions, we will present separate estimates of treatment effects for each site. In the case of statistically, but clinically marginally significant interactions, we will present main effect estimates of treatment effect but with interactions in the model using -1, 0, 1 dummy coding for site, so that the main effects' estimates will be for the average site.

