**Aims 1 & 2 (To assess whether PAI improves asthma control and other asthma outcomes):** The ITT effect of PA relative to UC on change in asthma control and other asthma outcomes since baseline at 6 months will be assessed with estimation and testing of the treatment-6 month visit interaction in the linear RE model (described above) with asthma control as the dependent variable. In addition, the treatment-12 month interaction will be tested and estimated to assess if the ITT effect is retained after the PA intervention ends.

**Secondary Aim 1 (Mediators):** The mediation analysis will follow the 4-step regression approach for testing mediated effects of Holmbeck. First, we will examine the association between PAI and mediators (D.8.2) by fitting separate longitudinal RE models with each mediator as the dependent variable. These models will test the effects of the PAI relative to the UC group with respect to change since baseline at each follow-up visit for the potential mediators. Second we examine the association between the PAI and asthma control as described in Aim 1. Third, we will assess the relationship between the mediators and asthma control by fitting separate longitudinal RE models with the mediators (D.8.2) as the independent variables and asthma control as the dependent variable. Finally, the mediators with significant effects at steps 1 and 3 will be included as a lagged time-varying covariate in the ITT linear RE model for asthma control in Aim 1. Mediators of the PAI will be assessed by comparing the randomization (intervention) effect estimate with and without the potential mediator in the model. A reduction of at least 15% in the treatment-visit interaction parameters at 6 and 12 months due to the inclusion of the mediator in the model will be the criteria for a significant mediator.

**Secondary Aim 2: Moderators** of the intervention (D.8.3) will be tested and estimated with 3- and 2-way interactions among the treatment factor, potential moderator, and visit factor in the ITT model in Aim 1. Similarly, moderators of the mediating relationship will be assessed with 3- and 2-way interactions among the treatment factor, mediator, potential moderator, and visit factor in the mediation model in Secondary Aim 1.

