**Specific Aim 3 (To estimate the incremental costs and incremental cost-effectiveness (ICE) of PA):** ICE will be assessed by comparing the incremental cost of PA (including both intervention costs, as well as costs of care) relative to UC per outcome, e.g. cost per day asthma control or avoided ED, hospitalization. The ICE will be determined based on differences in direct costs (payer perspective) and also including indirect

costs (societal perspective) and will be calculated based on differences in mean costs for the UC group from those in the PA group, divided by the mean difference in outcomes (asthma control, prednisone bursts, ED visits, hospitalizations, etc.). We also will calculate the incremental cost per quality adjusted life year as estimated from the AQOL. We will estimate statistical error and construct confidence intervals using bootstrap procedures for the incremental cost difference and the incremental cost-effectiveness ratio (ICER).

**Exploratory Aim (Post-study focus groups of providers):** Audio records and notes will be coded into categories emerging from the data by independent coders ([name], [name], [name]) who will achieve inter-coder reliability. Using the Grounded Theory approach, we will then analyze the agreed upon categories, and place them into themes emerging from discussions.

**D.10. Sample size:** We will enroll 300 adults (150 per intervention group). The primary outcome (Aim 1) is asthma control at Visit 3 (6 months) and Visit 5 (12 months). While a clinically meaningful difference in asthma control within-individual is 0.5, we expect the average difference across groups to be smaller. The WIN Study demonstrated a small difference in mean change of  $0.2 \pm 1.1$  in asthma control across intervention groups at Visit 8 (6 months). The effect was neither clinically nor statistically significant. A difference in mean change of 0.32 in asthma control was found in a study with a different focus, but the effect was not statistically significant, probably due to the small sample size.

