**Specific Aim 1:** The power analysis is based on the 2-sample t-test with adjustments for 3 or 5 repeated measures per participant. The adjustment for clustering by patient multiplies the estimated sample size under simple random sampling by a design effect,  $d=1+\rho(n-1)$ , where  $n$ =average number of visits per patient, and  $\rho$  is the patient intraclass correlation. We apply a conservative intraclass correlation of 0.30. The power analysis also takes into consideration the following factors: 1) 18% drop-out as observed in WIN; 2) adjusted 2-sided significance level of 0.025; and 3) 80% power. With these factors, the study is powered to observe a standardized effect of 0.29 and 0.32 difference in mean change in asthma control across intervention groups at 6 months and 12 months, respectively. **Specific Aim 2:** The power analysis examines the intervention effect on 5 asthma outcome measures at 6 and 12 months. Using the same assumptions but with 2-sided  $\alpha=0.005$  to conservatively adjust for multiple comparisons, we will have 80% power to detect a standardized effect of 0.34 and 0.31 between groups at 6 months and 12 months, respectively. **Specific Aim 3:** Power for the economic analysis (costs have greater variability than clinical outcomes) is 81% based on the same effect size, 2-sided  $\alpha$  of 0.05, an effect-cost correlation of -0.1, a difference in cost of \$500 and a willingness to pay (WTP) threshold of \$2500 per year of improved adherence or avoided hospitalization. An increase in the WTP to \$3000 results in 98% power. Thus, the sample size will provide sufficient statistical power for assessment of both clinical and economic evaluations (which requires detecting both effect and cost differences).

**D.11. Data Management:** The Clinical Research Computing Unit will collaborate to finalize CRFs, construct the database, protect its security, perform data entry, review, query and update data; assist with preparation of DSMB reports, and collaborate with biostatisticians as it has for HAP and WIN studies.

**D.12. The Data Safety Monitoring Board** (see Human Subjects) will meet at study start, year 2, and year 5. At these and every 6 months the DSMB will review reports of accrual, baseline comparability between PA and UC groups, adverse events, safety concerns, data quality, maintenance of confidentiality and recommend study modifications and whether the study can continue.

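### D.10's 80% power for Aim 2 belongs to an average over visits that includes baseline, not to the 6- and 12-month change-from-baseline tests named in D.9

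*Combined protocol and SAP*

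**What the plan says.** D.10 (Sample size) plans 150 per arm. For Aim 1, "The power analysis is based on the 2-sample t-test with adjustments for 3 or 5 repeated measures per participant". It multiplies the sample size by a design effect of 1 + rho(n-1), where n is the number of visits per patient, and adds: "We apply a conservative intraclass correlation of 0.30". It allows for 18% drop-out. For Aim 2, "The power analysis examines the intervention effect on 5 asthma outcome measures at 6 and 12 months"; the assumptions are unchanged except that two-sided alpha is 0.005, and the result is "we will have 80% power to detect a standardized effect of 0.34 and 0.31 between groups at 6 months and 12 months, respectively".

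D.10 places 6 months at Visit 3 and 12 months at Visit 5, and Table 1 makes Visit 1 the baseline. Three and five measures therefore include baseline.

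D.9 fits random effects models to baseline and every follow-up visit, with a separate treatment term for each follow-up visit, so that "the treatment-time interaction for a particular visit will be the ITT effect on change since baseline". For Aims 1 and 2 the test is of "The ITT effect of PA relative to UC on change in asthma control and other asthma outcomes since baseline at 6 months", by way of the 6-month interaction; the 12-month interaction is tested as well. Counts use a log-linear version of the model.

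**The concern.** Averaging several visits shrinks the standard error, and the repeated-measures adjustment in D.10 takes that credit. The D.9 test compares the arms on change since baseline at one visit, so most of the credit is not available to it. One of the averaged visits is also the pre-randomization baseline, where the intervention can have had no effect.

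If so, the 80% is attached to the wrong test. D.10 concludes that the sample is large enough for the clinical evaluations, and a reader relying on that could take a null Aim 2 result as evidence of no effect when the test had much less than 80% power at the stated effects.

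Three of the five Aim 2 outcomes (prednisone bursts, ED visits, hospitalizations) are counts. A t-test effect in SD units does not describe what a log-linear count model can detect.

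**Working it through.** **Inputs (all D.10).** 150 x 0.82 = 123 per arm; correlation 0.30; two-sided alpha 0.005; 80% power. The multiplier is 2.807 + 0.842 = 3.649, and 2/123 = 0.01626.

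**1. Reproducing the stated pair.** Detectable effect for an average of k visits = 3.649 x sqrt(2/123 x (1 + 0.30(k-1))/k).

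- k = 3: 3.649 x sqrt(0.01626 x 1.6/3) = 0.340 (stated 0.34)
- k = 5: 3.649 x sqrt(0.01626 x 2.2/5) = 0.309 (stated 0.31)

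Other routes miss the pair: one visit gives 0.465; 2 and 4 visits give 0.375 and 0.321; 150 per arm gives 0.308 and 0.280 (3 and 5 visits) or 0.340 and 0.290 (2 and 4 visits).

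**2. The D.9 tests, complete data.** I took the D.9 model with five visits, equal correlation 0.30 and a separate treatment term per visit, and solved it by generalized least squares with 123 completers per arm. The standard error (SE) of the 6- or 12-month interaction, in cross-sectional SDs, is:

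- with a treatment main effect at baseline: sqrt(2(1 - 0.30) x 2/123) = sqrt(1.4 x 0.01626) = 0.1509
- with equal baseline means: sqrt((1 - 0.30²) x 2/123) = sqrt(0.91 x 0.01626) = 0.1216

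It is the same with three visits as with five. To express effects in SDs of change, divide by sqrt(1.4) = 1.183, giving 0.1275 and 0.1028. Power = Phi(effect/SE - 2.807); detectable effect = 3.649 x SE.

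| Reading | SE | Power at 0.34, 6 months | Power at 0.31, 12 months | Detectable with 80% power |
|---|---|---|---|---|
| Main effect, cross-sectional SD | 0.1509 | 29% | 23% | 0.55 |
| Equal baseline, cross-sectional SD | 0.1216 | 50% | 40% | 0.44 |
| Main effect, SD of change | 0.1275 | 44% | 35% | 0.47 |
| Equal baseline, SD of change | 0.1028 | 69% | 58% | 0.38 |

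**3. Partial data.** D.9 keeps all randomized participants. The timing of drop-out is not given, so I assumed 4.5% of each arm is lost after each of Visits 1 to 4 (4 x 4.5% = 18%). With equal baseline means the SE is 0.1153 at 6 months and 0.1209 at 12 months in cross-sectional SDs, or 0.0975 and 0.1022 in SDs of change. Power in SDs of change is Phi(0.34/0.0975 - 2.807) = 75% and Phi(0.31/0.1022 - 2.807) = 59%. The detectable effects are 0.36 and 0.37.

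**4. Cross-check on Aim 1.** At alpha 0.025 the multiplier is 2.241 + 0.842 = 3.083. The averaging formula gives 0.287 (3 visits) and 0.261 (5 visits). D.10 says "the study is powered to observe a standardized effect of 0.29 and 0.32 difference in mean change in asthma control across intervention groups" at 6 and 12 months. The first matches; the 12-month 0.32 does not.

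**The case against.** **Units and model.** The lowest figures need cross-sectional SDs and a treatment main effect at baseline. D.9 lists treatment terms only for follow-up visits, which taken literally is the equal-baseline model. D.10 also leans towards SDs of change: "The WIN Study demonstrated a small difference in mean change of" 0.2 ± 1.1, and 0.29 x 1.1 = 0.32. This stands. A reader might infer that 23% is the power of the planned test; the documents do not support fixing on that reading.

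**Partial data.** A reader might also take 69% as the ceiling, or conclude that the extra visits add nothing. Both hold only for complete data; step 3 gives 75% at 6 months. With no drop-out at all (150 per arm), the most favourable reading reaches 80% at 6 months, but only 70% at 12 months. The stated pair needs 123 per arm at both times, so the plan does not assume that.

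**Correlation.** At an assumed 0.7, power with 123 completers is 74-82% / 63-72% in cross-sectional SDs, but 44-53% / 35-43% in SDs of change. The plan gives 0.30. At 0.7 its own averaging formula would give 0.42 and 0.41, so 0.7 cannot support the stated pair.

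**Event window.** A reader might infer that the plan leaves the period for counting events wholly undefined. That is too strong: D.6.1 asks at each quarterly visit about urgent care since the previous one, and the questionnaires sit in an appendix not included here. Only the baseline look-back, and whether the 6- and 12-month counts are per-visit or cumulative, remain unclear in the text available.

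**Conclusion.** The stated 80% does not belong to the tests D.9 names. At the plan's correlation of 0.30 and its 18% drop-out, applied at both time points or building evenly, no reading examined reaches 80% at the stated effects. On the most favourable one (equal baseline means, SDs of change, partial data used) the 6-month shortfall is small: 75%, with 0.36 detectable against 0.34. At 12 months it is clear on every reading: at most 59%, with 0.37 detectable against 0.31. These results rest on equal correlation between visits, the normal approximation and, for the partial-data figures, the assumed even drop-out.

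The mismatch of method applies to Aim 1 too, and its 12-month figure does not reproduce by D.10's formula. A reader should not infer that Aim 1 is short on every reading: with 123 completers, equal baseline means and SDs of change, the detectable effect at alpha 0.025 is 3.083 x 0.1028 = 0.317, close to the stated 0.32. The 0.32 may also be 0.29 converted to questionnaire points; D.10 does not say.

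**What to change.** In D.10, replace the Aim 2 power sentence with the power or detectable effect of the visit-specific tests in D.9. State whether the model has a treatment main effect at baseline, which SD standardizes the effect, the correlation, and how drop-out enters. For example: with 123 completers per arm, correlation 0.30 and two-sided alpha 0.005, each 6- or 12-month interaction has 80% power for 0.47 SD of change with a treatment main effect, or 0.38 with equal baseline means (0.55 or 0.44 in cross-sectional SDs). If partial data are credited, give the assumed drop-out pattern; even loss with equal baseline means gives 0.36 at 6 months and 0.37 at 12 months, in SDs of change.

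For ED visits, hospitalizations and prednisone bursts, give detectable rate ratios under stated event-rate assumptions in place of an SD effect. Restate Aim 1 on the same basis and say what its 0.32 measures.

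A short clarification of the baseline look-back, and of whether event counts are per-visit or cumulative, would help but is secondary.

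The cost is recalculation and wording, with no new participants or data. The downside is a less favourable stated figure.

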#### D. APPROACH

**D.1. Two studies, WIN and ongoing HAP**, motivate, inform, and support PAI's likelihood of success. These and other studies demonstrate our ability to recruit patients from low income urban neighborhoods with moderate or severe asthma and follow them for significant periods of time. All pertain to the patient-MD relationship beginning with a study of adherence which the IOM and our studies found to be a measure of the success of the patient-physician relationship.

**D.1.1. WIN Study: "Individualized Interventions to Improve Adherence in Asthma" (R01 HL073932; [name], PI),** a randomized controlled trial (RCT), compared problem-solving (PS) to asthma education (AE) to improve inhaled steroid adherence and asthma outcomes in adults with moderate or severe asthma recruited from clinics serving low-income urban neighborhoods. PS involves identifying specific barriers to adherence, proposing and weighing solutions, trying the best, assessing, and revising. Adherence was monitored electronically. 333 adults (English- or Spanish-speaking) were randomized: 49 $\pm$ 14 years, 72% female, 68% African American, 7% Latino, mean FEV1 66% $\pm$ 19%, 52% with ED visits, 31% with hospitalizations for asthma in the prior year. Comorbidities were common: hypertension in 52%, diabetes in 22%, mean BMI 33 $\pm$ 9. In an intention to treat (ITT) analysis, there was no difference between groups with respect to overall change in any outcome ( $p>0.20$ ). Mean adherence was 61%  $\pm$  27%. Both groups changed similarly from baseline: adherence declined overall by 12% but asthma control, asthma-related quality of life (AQOL), and FEV1 improved overall by 15%, 18%, and 6% respectively. ED visits and hospitalizations did not significantly decrease. While PS was not better than AE, monitoring adherence with provision of medications and attention to patients given to both groups was associated with improvement in some asthma outcomes. Electronic monitoring is not a real-world intervention. Changes in inhaler formulation will make current monitors obsolete. Thus, monitoring is unlikely to be a feasible or cost-effective intervention.

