**The Primary outcome is asthma control,** patient-oriented and the primary therapeutic goal emphasized by national and international guidelines for managing asthma and a recent Asthma Outcomes Workshop. Preliminary data from the HAP Study demonstrates overall improvement in asthma control (D.1.4). Other asthma-related patient-oriented outcomes: prednisone bursts, ED visits, hospitalizations, ICU admissions, and quality of life (D.8.1) will be collected.

In WIN and HAP Studies, electronically-monitored adherence to inhaled steroids was the primary outcome. In WIN, both groups improved and the monitoring process was a common intervention between problem-solving and asthma education groups. Monitoring had 3 elements that together improved asthma outcomes: attention, monitoring feedback, and provision of inhaled steroids necessary for electronic monitoring. Thus, although adherence is a measure of patient-provider communication, it is not an appropriate outcome to test the effectiveness of this pragmatic PAI. Additionally, monitored adherence is not patient-oriented or pragmatic. We will measure self-report of adherence, which is correlated to monitored adherence and more pragmatic although less precise (D.8.2).

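### D.10: the two Aim 3 power figures (81% at a WTP of $2,500, 98% at $3,000) cannot both follow from the planned effect sizes under the usual net-benefit formula

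*Combined protocol and SAP*

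**What the plan says.** All of this is in D.10 (Sample size) of the combined protocol and SAP, unless another section is named.

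- **Aim 1:** "the study is powered to observe a standardized effect of 0.29 and 0.32 difference in mean change in asthma control", at 6 and 12 months, for two-sided alpha 0.025, 80% power, 18% drop-out and an intraclass correlation of 0.30.
- **Aim 2:** standardized effects of 0.34 and 0.31, with alpha 0.005.
- **Aim 3:** "costs have greater variability than clinical outcomes) is 81% based on the same effect size". The other inputs are two-sided alpha 0.05, an effect-cost correlation of -0.1, a cost difference of $500 and a WTP of $2,500 "per year of improved adherence or avoided hospitalization". At $3,000 the text says this "results in 98% power. Thus, the sample size will provide sufficient statistical power for assessment of both clinical and economic evaluations", and adds that the economic evaluation is one "which requires detecting both effect and cost differences".

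Enrolment is 150 per group. Two methods references are attached to the Aim 3 power. The section does not print the formula, either SD, whether the $500 is an added cost or a saving, or the n analysed for Aim 3.

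**The concern.** A 20% rise in WTP is said to lift power from 81% to 98%. That is a steep climb for a trial planned on effects of about 0.3 SD. In a net-benefit test, power climbs that fast only when the effect is large relative to its SD and an added cost offsets much of its value at the lower WTP.

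D.10 uses the two figures to conclude that the sample size is adequate for the economic evaluation. Aim 3 is a Specific Aim, so an inconclusive cost-effectiveness result would be read against a claimed power of 81% to 98%. As printed, a reader cannot check that claim.

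**Working it through.** **1. Reproduce D.10's effect sizes.** Completers per arm: 150 × 0.82 = 123. Design effect 1 + 0.30(k - 1): 1.6 for 3 visits and 2.2 for 5. Effective n per arm: 123 × 3/1.6 = 231 and 123 × 5/2.2 = 280. Detectable d = (z for alpha + z for power) × sqrt(2/n).

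| Aim | Visits | Computed | Stated |
|---|---|---|---|
| 1 (alpha 0.025) | 3 | 0.287 | 0.29 |
| 1 | 5 | 0.261 | 0.32 |
| 2 (alpha 0.005) | 3 | 0.340 | 0.34 |
| 2 | 5 | 0.309 | 0.31 |

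Three of the four reproduce as standardized effects. The 0.32 does not, but nothing below depends on it, because 0.34 always gives the most favourable result.

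**2. Formula (assumed, since none is printed).** With W the WTP, dE and dC the differences in effect and cost, and sE and sC their SDs:

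z = sqrt(n/2) × (W·dE - dC) / sqrt(W²·sE² + sC² + 0.2·W·sE·sC); power = Φ(z - 1.96); d = dE/sE.

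The 0.2 is -2 × (-0.1). Both SDs are left free, and dC is tried as +500 and -500.

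**3. What the pair demands.** 81% needs z = 2.838 and 98% needs z = 4.014. Their ratio is 1.414, while W rises by a factor of 1.2.

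**4. If the $500 is a saving.** The numerator W·dE + 500 grows by less than 1.2 and the denominator does not shrink, so z rises by less than 1.2. From 81%, power at $3,000 stays below Φ(1.2 × 2.838 - 1.96) = 92.6%, whatever the effect size.

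**5. If the $500 is an added cost.** Two limits apply.

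- *Ceiling at any WTP:* ignoring the cost altogether, power cannot exceed Φ(d·sqrt(n/2) - 1.96). For n = 123 and d = 0.34 this is Φ(2.666 - 1.96) = 76%.
- *Smallest d giving both figures:* the most favourable case is sC = 0, where z(W) = sqrt(n/2) × (d - 500/(W·sE)). Since (1/2500)/(1/2500 - 1/3000) = 6, solving for d gives d = sqrt(2/n) × [z1 + 6(z2 - z1)]. Allowing for rounding (81.5% and 97.5%), z1 = 2.856 and z2 = 3.920, so the bracket is about 9.24. For n = 123: 0.1275 × 9.24 = 1.18.

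**6. Search over the unprinted SDs.** The effect SD was varied from 0.0001 to 10,000, with d = 0.29, 0.31, 0.32 and 0.34 and both cost directions. The cost SD was solved so that power at $2,500 is exactly 81%. The highest resulting power at $3,000 is in the third column.

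| n per arm | Source | Highest power at $3,000 (stated: 98%) | Ceiling at any WTP, added cost, d 0.29 to 0.34 | Smallest d giving both figures |
|---|---|---|---|---|
| 123 | 150 × 0.82 | 83% | 62–76% | 1.18 |
| 150 | enrolled | 84% | 71–84% | 1.07 |
| 231 | 123 × 3/1.6 | 86% | 88–95% | 0.86 |
| 280 | 123 × 5/2.2 | 86% | 93–98% | 0.78 |
| 341 | 150 × 5/2.2 | 88% | 97–99% | 0.71 |

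Allowing 79% to 83% at $2,500 raises the third column only to 85–89%. The last column is a floor. At n = 150, matching 81% and 98% exactly needs d = 1.14 with no cost variability, 1.36 when the cost SD equals the WTP-valued effect SD, and 1.83 when it is twice that. D.10 itself remarks that costs vary more than clinical outcomes.

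**The case against.** **The formula is assumed and the cited papers are not to hand.** This stands, and it limits the claim to the usual net-benefit test. But a WTP, an effect-cost correlation and a cost difference are the inputs of that test. The remark about needing to detect both differences might suggest two separate tests, one of effect and one of cost. WTP enters neither, so power could not then move from 81% to 98% with WTP.

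**The effect may not be standardized.** D.10's wording for Aim 1 is loose. Since 0.29 × 1.1 (the WIN SD for asthma control) = 0.319, the 0.32 could be a raw difference. On that SD it is still 0.29 SD, so the pair still fails. A standardized value entered by mistake as a raw effect with a small SD would recover the pair, and this is one possible cause. The documents do not confirm it.

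**A reader might go further** and link the WTP unit to the WIN adherence SD of 27% (D.1.1), concluding that Aim 3 was powered on a 32-point adherence difference. That does not hold up. With a raw 0.32 and an added cost, an SD of 0.27 gives 96.7% at n = 123 and 97.3% at n = 150. At n = 231 any effect SD from 0.20 to 0.32 fits. Raw effects from 0.28 to 0.36 also fit, and the WTP unit names avoided hospitalization as well.

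**81% may be right, and Aim 3 may be well powered.** 81% alone is attainable for some SDs and n. The 62–76% ceiling belongs only to 123 per arm with an added cost; at an effective n of 231 it is 88–95%. D.2.2 expects higher initial resource use but allows for offsetting savings, so the direction is open. The documents therefore do not support saying that Aim 3 is underpowered.

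**Conclusion.** The point holds for the pair of figures. Under a net-monetary-benefit test with D.10's alpha, correlation and cost difference, effects of 0.29 to 0.34 cannot give both 81% at $2,500 and 98% at $3,000, for any cost or effect SD, either cost direction and any n from 123 to 341 per arm. Given the first figure, the second is at most 83–88%. The pair needs a standardized effect of at least about 0.7 to 1.2, and more once cost variability is allowed for. Reversing the sign of the correlation or using a one-sided alpha does not change this.

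The conclusion rests on the assumed formula and on taking D.10's statement that the effect size is the same at face value. The consequence is confined to the economic part of the adequacy claim. The 300 is argued first from asthma control, and D.9 already plans bootstrap confidence intervals for Aim 3.

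**What to change.** Recompute Aim 3 power and print in D.10:

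- the formula;
- the n after 18% drop-out, and whether any repeated-measures adjustment is applied;
- the direction of the $500;
- the cost SD, as a range;
- the effect difference and its SD in the WTP unit.

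Reconcile that unit with the Aim 3 outcomes in D.9. These name asthma control, prednisone bursts, ED visits and hospitalizations, and leave the list open without naming adherence. On adherence, D.2.2 says "it is not an appropriate outcome to test the effectiveness of this pragmatic PAI".

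Replace the 81%, the 98% and the economic half of the adequacy statement with the result, or with the expected confidence-interval width for net benefit.

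The cost is one recalculation and some protocol wording. No extra patients are needed and the analysis does not change. The restated figure will probably be less favourable.
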